2.1 Background & Aims

Chronic ankle instability (CAI) is the most common musculoskeletal injury in sports and the rate of CAI accounts for 85% of ankle injuries. It has been estimated that 23,000 ankle sprains occur each day in the United States, representing approximately 1 sprain per 10,000 people per day and nearly one in five ankle injuries result in chronic symptoms. Numerous researchers applied mindfulness for improving the performance of various sports such as table tennis, shooting, cricket, archery, golf, swimming, and cycling. Since many of the players do not possess effective pain coping skills, they are at risk for lifelong impairment of their emotional, social, and physical functioning. Mindfulness-centered interventions may well serve to mitigate pain-related disability. Training in mindfulness meditation improves anxiety, depression, stress, and cognition. Mindfulness-related health benefits are associated with enhancements in cognitive control, emotion regulation, positive mood, and acceptance, each of which have been associated with pain modulation. Since mindfulness has been proven effective in managing various health disorders and in enhancing sports performance, our study aims to apply the mindfulness approach in rehabilitating the most common sports injury, CAI. The improvement in CAI due to the mindfulness approach will be assessed by the improvement in pain response through the Cumberland ankle instability tool, Functional ankle disability index (FADI), Visual analog scale (VAS), Brief Pain Inventory (BPI), Y-balance test, Mindfulness attention awareness score (MAAS), Oxford Happiness Questionnaire (OHQ) quantitative electroencephalography (Q-EEG). This study finding will be useful in assessing the effectiveness of mindfulness in rehabilitating CAI and identify the correlation of CAI pain response with VAS & BPI, quantitative electroencephalography - Q-EEG. In this clinical trial, we wish to use noninvasive methods such as quantitative EEG (electroencephalogram) to find the brainwave patterns during the different stages of

mindfulness intervention (pre and post). The outcome of this study will eventually lead to the identification of a better assessment method to indicate the pain response for the appropriate physiotherapy management. The application of mindfulness technique in CAI management and the usage of Q- EEG to assess the pain response in chronic ankle injury athletes are the novel approaches of this research study.

2.2 Background Literature Review

Chronic ankle pain can affect all age groups, ranging from young athletes to elderly patients with degenerative joint and soft-tissue disorders. As nearly one in five ankle injuries result in chronic symptoms¹. Approximately 60 percent of the injuries occurred in players younger than 20 years of age. The majority of injuries (91.5 percent) were categorized as mild overuse injury and mostly involved the knee and ankle. The majority of the injuries were diagnosed in younger players and occurred during training/practice sessions². Athletes who sustained an injury are potentially at the risk of developing major depressive and posttraumatic stress disorders. The injured athletes suffer from depression 6 times more in chances as compared to the non-injured athletes³. Besides, the injured athletes also exhibit greater anxiety and lower self-esteem. In chronic sports injuries, the athletes are more likely to become depressed than the counterpart. Practicing in elite level sports offers an entirely different set of circumstances, representing a high-pressure career replicate with stressors and constraints that tend to cause injuries to the athletes⁴.

In accordance to Putukian, (2016) stress is an important antecedent to injuries and can play a role in the response to, rehabilitation and return to play after injury⁵. The psychological response to injury can trigger and/or unmask mental health issues including depression and suicidal ideation, anxiety, disordered eating, and substance use/abuse. There are barriers to mental health treatment in athletes. They often consider seeking help as a sign of weakness, feeling that they should be able to ‘push through’ psychological obstacles as they do physical activities. Athletes may not have developed healthy coping behaviors making response to injury. Shivarathre et al., (2014) showed a significant association of anxiety, depression, and neuroticism in patients presenting with chronic foot and ankle pain⁶.

Mindfulness meditation has been found to improve a wide spectrum of cognitive and health outcomes. Training in mindfulness meditation improves anxiety, depression, stress, and cognition. Mindfulness-related health benefits are associated with enhancements in cognitive control, emotion regulation, positive mood, and acceptance, each of which have been associated with pain modulation. A pilot study by Schmidt et al., (2015) using 8-week mindfulness-based stress reduction (MBSR) program on a sample of low back pain patients was conducted in order to assess the feasibility and effectiveness of the intervention as well as changes in an EEG pattern called thalamocortical dysrhythmia which is associated with chronic pain⁷. For a full MBSR course, it can take up to eight weeks, with weekly meetings that last for about three hours and daily practice of about an hour⁸. This can be difficult to adhere to especially in the current fast-paced lifestyle of young people⁹. With due consideration with participants’ compliance, the mindfulness intervention practice of the present study has been modified to 3- min video assisted mindfulness deep breathing. Furthermore, the follow up of participants’ home practices will be monitored with the use of a smartphone app which has the facility to send reminders as text messages to fill in the

practice diaries or online portals to record the frequency of home practice of our intervention. We wish to apply the video assisted mindful deep breathing combined with standard physiotherapy to find the effectiveness of the interventions in attention process to reduce the incidence of reoccurrence of chronic ankle instability.

3 Study Protocol

3.1 Research Design Outline

The study aims to perform a randomized control trial on CAI participants in INTI physiotherapy centre and compare with healthy controls as a causal comparative study

Study 1 (Formerly titled “Effect of short duration video assisted mindful deep breathing among collegiate athletes with chronic ankle instability – a Randomised Control Trial”) involves participants with chronic ankle instability by using the Cumberland Ankle Instability Tool (CAIT)¹⁰, if the score was ≤ 27 in the CAIT tool over 30 by fulfilling the inclusion criteria.

Study 2 is a causal comparative study, which involves age matched healthy collegiate athlete from local university and compared them with the baseline parameters of Study 1.

The proposed study designs are all investigator blinded in the randomized control trials (Study 1). Participants only be involved in Study 1 and baseline measurements are compared with Study 2.

3.2 Participants

Study 1 and 2

University students those who involved in collegial sports with chronic ankle instability and without chronic ankle instability/musculoskeletal injuries from INTI International University at Malaysia will be eligible to participate in this study.

Study investigators will not be eligible to participate.

Participants randomized to experimental group in the study 1 will require a personal android support hand phone to the install the VAMDB from the google app store to participate.

3.3Recruitment

Study 1

All participants with chronic ankle instability (CAI) attending the INTI physiotherapy centre will be enrolled in the study at Phase 1. The participation information and consent sheet will be distributed which details including inclusion and exclusion criteria. Interested CAI participants will be invited to undergo baseline assessments (pain – Visual analog score (VAS), Brief pain inventory (BPI); Balance – Cumberland ankle instability tool (CAIT), functional ankle disability index (FADI) and Y-balance test; psychology – mindfulness attention awareness score (MAAS) and oxford happiness questionnaire (OHQ); quantitative EEG) with scheduled appointments.

All participants will have to return a signed consent form to the physiotherapy centre officer to random allocation to a study group.

Study 2

All participants without chronic ankle instability (CAI)/ musculoskeletal injuries will be invited by flyers and sending an invitation to University sports club. The participation information and consent sheet will be distributed which details including inclusion and exclusion criteria. Interested CAI participants will be invited to undergo baseline

assessments (Balance – Cumberland ankle instability tool, functional ankle disability index; psychology – mindfulness attention awareness score and oxford happiness questionnaire; quantitative EEG) with scheduled appointments. All participants will have to return a signed consent form to physiotherapy centre officer for allocation to a study group

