3.4 Randomization

Collegiate athletes with CAI who consent to participate will be randomly allocated (within their study) to one of two groups (at a ratio of 1:1): the intervention, the standard physiotherapy, and short duration video assisted mindful deep breathing + standard physiotherapy. Whereas the participants without CAI (healthy age matched control) will be allocated to group 3 as healthy controls.

Computer randomisation (<http://www.graphpad.com/quickcalcs/index.cfm>) and concealed envelopes will be used for CAI participants.

Participants will be allocated a unique identification number, and this will be recorded against their identification number allocation in an electronic database. This will be done by the INTI physiotherapy centre maintenance officer to ensure the investigators remain blinded.

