3.5 Administration

Study 1

Participants allocated to experimental and experimental control group will be given the appropriate access for 12 weeks (instructions provided in the study envelope). Participants will be encouraged to attend the regular appointments for 5 times a week for 6 weeks intervention and follow up (week12) in INTI international university physiotherapy centre. At

the end of week 3, end of week 6 and end of week 12 instructed to participate in post intervention assessments the duration of waiting time and assessment time will be clearly stated under the guidelines.

Study 2

Participants allocated to healthy control group will be given the appropriate access for baseline assessment (instructions provided in the study envelope)

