3.7 Sample Size

Study 1

G*power was utilized for sample size calculation with equal group sizes (i.e ratio of groups 1:1). A total of 36 participants with CAI (i.e. 18 in each group) to be able to reject the null hypothesis that the population means of the experimental and control groups are equal with probability (power) 0.95. The Type I error probability associated with this test of this null hypothesis is 0.05¹¹.

- Assuming a total drop-out rate of 10%, we will recruit 20 subjects for each group, i.e. 20 experimental and 20 experimental control group.

Study 2

A total of 20 participants without CAI will be recruited and compared with the age matched CAI participants in the study 1.

4. Statistical Analysis Plan (SAP)

All Studies

Descriptive and inferential statistics will be used. Normally distributed data will be presented by mean and standard deviation (SD) and non-normally distributed data will be presented by median and interquartile range. Categorical data will be presented using percentages. SPSS (version 22.0) will be used for all statistical analyses.

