4.3 Missing Data

For participants who are randomized and do not attend for assessment, a mean imputation of the assessment scores from their allocation group will used.

5. Informed Consent Forms (ICF)

Study 1

Written consent will be gained from the study participants with CAI using the consent forms attached to the application.

Study 2

Written consent will be gained from the study participants without CAI using the consent forms attached to the application.

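### Section 3.2 sets the Android phone requirement only for participants already randomised to the experimental group, so any loss or non-use it causes would fall on that arm alone

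*Protocol*

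**What the plan says.** Section 3.2 opens with a general eligibility statement for university athletes that does not mention a phone. It then adds a condition for one arm: "Participants randomized to experimental group in the study 1 will require a personal android support hand phone". The phone is needed for the study app, and the same sentence makes this a condition of taking part. Nothing comparable is stated for the control arm.

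Section 3.3 describes how athletes reach randomisation. On the criteria it says: "The participation information and consent sheet will be distributed which details including inclusion and exclusion criteria". The step before allocation is consent: "All participants will have to return a signed consent form to the physiotherapy centre officer to random allocation to a study group". Section 3.4 agrees: "Collegiate athletes with CAI who consent to participate will be randomly allocated (within their study) to one of two groups". Neither section mentions a phone.

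Two other places bear on what the app does. Section 2.2 describes it as a means of following home practice, with reminders to complete diaries. Section 3.5 says: "Participants allocated to experimental and experimental control group will be given the appropriate access for 12 weeks". It schedules visits to the centre five times a week for six weeks, but does not say whether the video can also be used there.

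**The concern.** Randomisation makes the arms comparable on everything settled before allocation. Owning an Android phone is settled before allocation, so athletes without one should be spread over both arms by chance. A requirement that binds only one arm, and only once the arm is known, acts on those athletes in that arm and leaves their counterparts in the other arm untouched.

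Two things could follow. Athletes without a phone might leave the experimental arm, so that its completers are phone owners while the control arm remains a mixture. Or they might stay and be assessed without having used the app, so that the contrast between the arms is weakened. The protocol does not say which would happen. With 20 per arm, each athlete affected is 1/20 = 5% of the arm.

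**Working it through.** **1. The plan's own figure.** Section 3.7 needs 18 per group and says: "Assuming a total drop-out rate of 10%, we will recruit 20 subjects for each group". Check: 18 / (1 − 0.10) = 20, and 20 × 0.90 = 18. The figure reproduces. It allows for 2 losses in each arm, the same in both. A loss caused by the phone requirement is of another kind, because it can arise in one arm only.

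**2. Order of events in the visible text.**

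| Step | Section | Phone condition stated? |
|---|---|---|
| General eligibility | 3.2 | No |
| Information and consent sheet with the criteria | 3.3 | Unknown; sheet not at hand |
| Baseline assessment and signed consent | 3.3 | No |
| Allocation by concealed envelope | 3.4 | No |
| Allocated to standard physiotherapy | 3.2 | No |
| Allocated to the experimental group | 3.2 | Yes |

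The only stated condition comes after allocation, in one arm.

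**3. What that does to the comparison.** Let p be the share of randomised athletes without a suitable phone. The expected number is 20p in each arm, but the requirement touches 20p in the experimental arm and 0 in the control arm. The documents do not give p. Purely as an assumed range, p = 10%, 20%, 30% or 40% would mean 2, 4, 6 or 8 of 20.

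- *If they leave.* Let δ be the difference in mean outcome between athletes without and with a phone, apart from any treatment effect, and Δ the treatment effect. The experimental arm then has mean μ + Δ, and the control arm μ + pδ. The observed difference is Δ − pδ, so the bias is −pδ. It is zero if p = 0 or if phone ownership is unrelated to outcome (δ = 0).
- *If they stay without the app.* Let f be the fraction of the benefit they still receive. The observed difference is Δ × [1 − p(1 − f)]. There is no dilution if f = 1, for example if the video is fully available at the centre.

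The documents give none of p, δ or f, so neither expression can be turned into a number.

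**4. With the condition applied to everyone before allocation.** Only phone owners are randomised, so p = 0 in both arms and both expressions reduce to Δ. The planned 20 + 20 does not change.

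**The case against.** The strongest objection is that the criteria are said to be in a sheet that is not at hand. It may list the phone as a criterion for all of Study 1, and its absence from the text reviewed is not evidence that the check is missing from the plan. This stands. In that case what remains is a sentence in 3.2 that disagrees with the sheet and should be aligned with it.

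Second, the sentence sits in the section on participants, ahead of recruitment, and may be meant as advance notice, so that an athlete without a phone could decline before randomisation. That is possible, and no section says when phones are checked. But the sentence binds only the experimental group, so as worded an athlete without a phone remains eligible and may consent.

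Third, non-use may matter little: 2.2 gives the app a monitoring and reminder role, and 3.5 has frequent visits to the centre. This also stands, and is a reason not to assume that athletes without the app receive nothing.

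A reader might infer more than the text supports:

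- *That athletes without a phone will be withdrawn, or that the result will be biased.* No section says anyone is withdrawn, and bias also requires phone ownership to be related to outcome.
- *That the harm can be sized through 4.3*, which says: "For participants who are randomized and do not attend for assessment, a mean imputation of the assessment scores from their allocation group will used". Filling in own-group means does make the test too liberal, but it does so for a loss of any cause and already at the planned drop-out. It is a separate defect and does not measure this one.

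**Conclusion.** The point holds as a minor one. Section 3.2, as written, places the phone requirement after allocation and on the experimental arm only, and the visible route to randomisation in 3.3 and 3.4 has no phone check. Any loss or non-use the requirement causes would therefore be confined to that arm.

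Its size cannot be given. The number affected, the bias and the dilution all depend on quantities that the documents do not state, and each could be zero. The conclusion rests on the literal wording of 3.2 and on the criteria sheet not already containing the check for both arms. If the sheet does contain it, the trial is protected and only the wording of 3.2 is at fault.

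**What to change.** Replace the sentence in 3.2 with an eligibility condition for all Study 1 participants, for example: *Every Study 1 participant must own a personal Android phone able to run the study app; this is confirmed before the allocation envelope is opened.* Put the same wording in the criteria sheet named in 3.3 or, if the sheet already has such a check, make 3.2 match it.

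The cost is a reworded sentence and one screening question before allocation. The sample size, arms and assessments stay as they are. The downside is a smaller eligible pool, by an amount the documents do not allow to be judged, at a single university that has to supply 40 athletes with CAI. The results would also apply to athletes who own such a phone. The fix does not repair the imputation rule in 4.3, which needs its own change.

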3.4 Randomization

Collegiate athletes with CAI who consent to participate will be randomly allocated (within their study) to one of two groups (at a ratio of 1:1): the intervention, the standard physiotherapy, and short duration video assisted mindful deep breathing + standard physiotherapy. Whereas the participants without CAI (healthy age matched control) will be allocated to group 3 as healthy controls.

Computer randomisation (<http://www.graphpad.com/quickcalcs/index.cfm>) and concealed envelopes will be used for CAI participants.

Participants will be allocated a unique identification number, and this will be recorded against their identification number allocation in an electronic database. This will be done by the INTI physiotherapy centre maintenance officer to ensure the investigators remain blinded.

3.5 Administration

Study 1

Participants allocated to experimental and experimental control group will be given the appropriate access for 12 weeks (instructions provided in the study envelope). Participants will be encouraged to attend the regular appointments for 5 times a week for 6 weeks intervention and follow up (week12) in INTI international university physiotherapy centre. At

the end of week 3, end of week 6 and end of week 12 instructed to participate in post intervention assessments the duration of waiting time and assessment time will be clearly stated under the guidelines.

Study 2

Participants allocated to healthy control group will be given the appropriate access for baseline assessment (instructions provided in the study envelope)

3.6 Assessment & Outcomes Measures

Study 1

Chronic ankle Instability (CAI) participants will be assessed for:

1. Primary outcomes
 - Cumberland Ankle Instability Tool (CAIT)
 - Ankle stability will be assessed by validated 9-item Questionnaire, to find the chronic ankle disability score among participants and to recruit in the study if the score was ≤ 27 in the CAIT tool over 30.
 - Y-balance test (YBT)
 - The dynamic balance of the participants will be assessed using reliable and validated the Y balance test (YBT) by measuring the distance in anterior, posterolateral, and posteromedial directions.
 - Visual analog scale (VAS)
 - CAI participants pain intensity will be record by self-reported pain intensity on a 10 cm line to point out the pain level. The point at 0 cm represents "no pain" and 10 cm represents "worst pain".
 - Brief Pain Inventory (BPI)

- Besides VAS, pain intensity and pain interference will be recorded using 4-items (worst pain, least pain, average pain, and pain right now) to measure the pain intensity, and 7-items (general activity, mood, walking, normal work, relations, sleep, enjoyment of life) to assess the pain interference. The participants will be instructed to report the pain intensity from 0 (no pain) to 10 (as pain bad as you can imagine). Similarly, the pain interference is recorded from 0 (does not interfere) to 10 (completely interferes)
- Mindful Attention Awareness Scale (MAAS)
 - CAI participants will be assessed by 15-item questionnaire to identify the participants' mindfulness level during the ankle instability.
- Oxford Happiness Questionnaire (OHQ)
 - Happiness level of CAI participants will be assessed using the Oxford Happiness Questionnaire (OHQ), which consists of a 29-item questionnaire.
- Functional ankle disability index (FADI)
 - CAI participants will be asked to complete 34-item questionnaire used to check the participant's general daily activity and sports specific functions for physical function and disability.

2. Secondary outcomes

- Non-invasive wireless electroencephalogram (EEG)
 - EEG will be used at 14 positions: AF3, AF4, F3, F4, F7, F8, FC5, FC6, P7, P8, T7, T8, O1, and O2. The EEG recordings of the CAI participants will be collected between 9 and 12 hours in the morning to reduce participants sleeping artifacts and to exclude the EEG from the influence of circadian variables. The EEG recordings will be recorded in eyes closed and eyes

open for 2mins.

The time commitment required of participants for assessment will be approximately 60 mins.

Study 2

Healthy control participants will be assessed for:

1. Primary outcomes

- Cumberland Ankle Instability Tool (CAIT)
 - Ankle stability will be assessed by validated 9-item Questionnaire, among participants and to recruit in the study if the score was >27 in the CAIT tool over 30.
- Functional ankle disability index (FADI)
 - Participants will be asked to complete 34-item questionnaire used to check the participant's general daily activity and sports specific functions for physical function.
- Mindful Attention Awareness Scale (MAAS)
 - Participants will be assessed by 15-item questionnaire to know the mindfulness attention level.
- Oxford Happiness Questionnaire (OHQ)
 - Happiness level of participants will be assessed using the Oxford Happiness Questionnaire (OHQ), which consists of a 29-item questionnaire.

2. Secondary outcomes

- Non-invasive wireless electroencephalogram (EEG)

- EEG will be used at 14 positions: AF3, AF4, F3, F4, F7, F8, FC5, FC6, P7, P8, T7, T8, O1, and O2. The EEG recordings of the participants will be collected between 9 and 12 hours in the morning to reduce participants sleeping artifacts and to exclude the EEG from the influence of circadian variables. The EEG recordings will be recorded in eyes closed and eyes open for 2mins.

The time commitment required of participants for assessment will be approximately 45 mins.

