4.1 Primary Outcomes

Study 1

The primary analyses will compare: (1) experimental vs experimental control group guidelines on their mean and standard deviation: (i) pain score (VAS & BPI), (ii) balance scores (CAIT & FADI), (iii) mindful attention (MAAS), and (iv) happiness scores (OHQ). Comparisons will be made using an unpaired t-test or a Mann-Whitney test for parametric and non-parametric data, respectively. P-values <0.05 will be considered statistically significant.

2*4-Repeated measures analysis of variance (ANOVA) will be performed to test the significant difference in the intervention effects between the time intervals (baseline, mid-intervention, post-intervention, and follow-up) and also between the two groups (Experimental control group and Experimental Group).

The post-hoc analysis will be conducted to investigate significant effect within the time intervals. Condition on if the sphericity violated (p-value < 0.05), the Greenhouse- Geisser estimated correction will be applied.

Effect sizes for will be calculated using Cohen's d (d) with 95% confidence intervals (95%CI) using the 'effsize' package¹². Effect sizes will be considered small if $0.2 \leq d < 0.5$, medium if $0.5 \leq d < 0.8$, and large if $d \geq 0.8$.

Study 2

The primary analyses will compare: (1) CAI participants vs healthy control group guidelines on their mean and standard deviation: (i) balance scores (CAIT &FADI) (ii), mindful attention (MAAS) and (iii) happiness scores (OHQ). Comparisons will be made using an unpaired t-test or a Mann-Whitney test for parametric and non-parametric data, respectively. P-values <0.05 will be considered statistically significant.

Effect sizes for will be calculated using Cohen's d (d) with 95% confidence intervals (95%CI) using the 'effsize' package¹². Effect sizes will be considered small if $0.2 \leq d < 0.5$, medium if $0.5 \leq d < 0.8$, and large if $d \geq 0.8$.

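### Y-balance reach is a primary outcome with no leg length listed for collection and no index ankle stated, which can cost precision in single-visit comparisons and leaves the tested limb open

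*Protocol*

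**What the plan says.** Section 3.6 (Study 1) lists the Y-balance test among seven primary outcomes. The only scoring given is that dynamic balance is assessed "by measuring the distance in anterior, posterolateral, and posteromedial directions". No scaling to body size, summary over directions, stance limb or trial rule follows.

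Section 3.3 lists the baseline assessments. The balance group reads "Balance – Cumberland ankle instability tool (CAIT), functional ankle disability index (FADI) and Y-balance test"; the others are VAS, BPI, MAAS, OHQ and quantitative EEG. Leg length and height appear neither there nor in 3.6.

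Eligibility rests on the CAIT, "to recruit in the study if the score was ≤ 27 in the CAIT tool over 30", with no mention of which ankle is scored or what happens if both qualify.

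For the analysis, section 4.1 names as the second group of scores "ii) balance scores (CAIT & FADI"; the Y-balance test is not named. The between-group test has no covariate: "Comparisons will be made using an unpaired t-test or a Mann-Whitney test for parametric and non-parametric data, respectively". The longitudinal analysis includes baseline: "2*4-Repeated measures analysis of variance (ANOVA) will be performed to test the significant difference in the intervention effects between the time intervals". Cohen's d with a 95% confidence interval is to be reported.

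**The concern.** The Y-balance test is the only primary outcome in Study 1 that measures physical performance; the other six are self-reported. Two things about it are left unsettled, and both are decided at the visit rather than in the analysis.

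- **Body size.** A longer-legged athlete reaches further at the same level of balance. An unadjusted comparison of raw distance at one visit therefore includes variance unrelated to treatment. With about 20 per arm, sex or height can also differ between arms by chance. If leg length is never recorded, no later analysis text can express reach relative to it.
- **Limb.** Chronic ankle instability can affect one side. If the ankle that qualified the athlete is not fixed as the one analysed, the score could come from the other limb or from an average of both. The choice could also be made after the data are seen.

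At stake is the power and interpretability of one primary outcome.

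**Working it through.** **1. The plan's own figure.** Section 3.7 states "A total of 36 participants with CAI (i.e. 18 in each group", power 0.95 and Type I error 0.05. It gives no effect size, SD, outcome or test, so 36 cannot be reproduced from stated inputs. Solving backwards:

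- Two-sample t-test, 18 per arm, power 0.95: d = 1.24 two-sided (1.12 one-sided).
- 2×4 repeated-measures interaction, assuming f = 0.25 and correlation 0.5: power 0.952 at N = 36 and 0.939 at N = 34.
- Drop-out: 36 / 0.9 = 40, or 20 per group, as stated.

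I use d = 1.24 (implied by the stated power) and d = 0.8 (the document's threshold for a large effect). The effect is defined on the size-normalised score.

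**2. Body size, single-visit t-test.** The documents give no leg-length variance, so its share R² of raw reach variance is an assumption. If the normalised effect is d, the effect on raw distance is d × √(1 − R²). For example, 0.8 × √0.5 = 0.57. Two-sided power at 0.05, 18 per arm:

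| R² | d = 0.8 | d = 1.24 |
|---|---|---|
| 0 | 65% | 95% |
| 10% | 60% | 93% |
| 25% | 52% | 88% |
| 40% | 44% | 80% |
| 50% | 38% | 72% |

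A second route uses physical units. Assume mean leg length 88 cm with SD 4–6 cm, reach 90% of leg length, and normalised SD 6–8% of leg length. Raw SD = √[(0.9 × SD_leg)² + (SD_norm × 88)²].

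- SD_leg 4 cm, SD_norm 8%: √(3.6² + 7.04²) = 7.91 cm against 7.04 cm. Variance ratio 1.26; 0.8 becomes 0.71; power 55%.
- SD_leg 6 cm, SD_norm 6%: √(5.4² + 5.28²) = 7.55 cm against 5.28 cm. Variance ratio 2.05; 0.8 becomes 0.56; power 37%.

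These ratios correspond to R² = 1 − 1/1.26 = 21% and 1 − 1/2.05 = 51%, in line with the table.

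**3. Chance imbalance.** Suppose 12 of 20 men in one arm and 8 of 20 in the other, with an assumed 7 cm sex difference in leg length. The raw mean difference shifts by (0.6 − 0.4) × 7 × 0.9 = 1.26 cm, about 0.16–0.17 of the raw SDs above.

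**4. Body size, group-by-time interaction.** Leg length is constant over the four visits, so it drops out when each person's own mean is subtracted. A simulation confirmed this (4000 runs, 18 per arm, effects of 0, 0.3, 0.6 and 0.6 SD at the four visits, correlation 0.5 before leg length is added):

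| Leg-length share | Interaction | t-test, third visit |
|---|---|---|
| 0% | 39% | 42% |
| 20% | 39% | 34% |
| 40% | 38% | 28% |
| 50% | 37% | 24% |

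The simulation standard error is √(0.39 × 0.61 / 4000) = 0.8 points, so the interaction column is flat within error.

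**5. Limb.** Suppose the analysed reach carries only a fraction w of the effect on the affected limb. Power with the effect multiplied by w:

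| w | t-test, d = 1.24 | t-test, d = 0.8 | Interaction, f = 0.25 |
|---|---|---|---|
| 1 | 95% | 65% | 95% |
| 0.75 | 77% | 42% | 75% |
| 0.5 | 44% | 22% | 39% |

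Unlike leg length, this dilution does not cancel in the interaction. The row w = 0.5 is averaging both legs when the effect is confined to one.

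**The case against.** A reader might infer that the unaffected limb and body size do enter this outcome and hide a treatment effect. The documents do not support that.

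- The text leaves the limb open. It does not say that the sound limb is tested or that sides are averaged.
- Section 3.3 says the participant information and consent sheet details the inclusion and exclusion criteria. That sheet is not in the text available, and an affected-ankle rule could be there. The limb point therefore holds only for the visible text.
- Both arms receive standard physiotherapy, and the randomised difference is mindful deep breathing, which section 2.2 expects to work through attention. Such an effect need not be confined to one leg, so halving is a worst case.
- Under randomisation, body size adds noise and chance imbalance, not systematic bias, and the planned interaction is protected from it.
- Section 4.1 does not name the Y-balance test among the scores for the unpaired comparison, so the test most exposed is not clearly assigned to it.
- Baseline reach is already collected. Adjusting for it would remove much of the stable body-size variance without leg length.

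All of this stands, and it limits the size and certainty of the harm. It does not remove the point. A primary outcome with no named analysis is not thereby protected, and the ANOVA's between-group main effect carries the same body-size noise as the t-test. Scoring detail can be left to a later plan, but a measurement that was never taken and a stance limb already used cannot.

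**Conclusion.** The point holds as a limited design weakness in one of seven primary outcomes. Reach is defined only as a distance, leg length is not listed for collection, and no index limb is stated in the visible text.

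- Any unadjusted single-visit comparison, and its Cohen's d, can lose precision. The loss is about 5–27 points of power at d = 0.8, or 2–23 points at d = 1.24, if leg length explains 10–50% of raw reach variance. Chance body-size imbalance can add a shift that is small in the example above.
- The group-by-time interaction loses essentially nothing to body size.
- The open limb choice could dilute an effect in every planned test, by an amount that depends on how far the effect is limb-specific.

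All the variance shares, effect sizes and dilution fractions are assumptions; the documents supply none of them. Study 2 is untouched on the Y-balance point, because its controls do not take that test.

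**What to change.** - **3.3 and 3.6:** record leg length once at baseline and define the Y-balance score as reach divided by leg length × 100. At minimum, adjust the comparison for the baseline reach already collected.
- **3.6:** fix the index ankle before randomisation: the qualifying ankle, or the one with the lower baseline CAIT if both qualify. Use it for both Y-balance and CAIT at every visit. If the information sheet already holds such a rule, bring it into the protocol.
- **4.1:** name the Y-balance score, including how the three directions are summarised, and its analysis.

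The cost is one short tape measurement within an assessment of about 60 minutes, one data field and a few lines of protocol text. Sample size and visit schedule do not change.
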